## **7.0 Expected Risks/Benefits**

Although the medication treatments, behavioral treatments and assessments to be administered in this study have been extremely well studied, including in individuals with CUD, and a favorable risk/benefit profile is expected, there are still possible risks. Risks, protections against risks, and benefits are described below.

### Potential Risks and Protections Against Risks:

*1. Emotional discomfort from questionnaires or tasks:* Some of the questions asked may be considered sensitive information, including drug use history and psychiatric symptoms. Answering these questions may be psychologically discomforting to some subjects. To reduce this risk, we make clear that we ask for sensitive information as part of the consent process. Similarly, some of the pictures used in the behavioral tests contain emotionally negative material (e.g. war scenes, attacks) that may be mildly upsetting to some subjects. Participants will be informed during the consent process that they may view such pictures, will be asked to report to the research assistant if they have any particular phobias or triggers, and told to inform the research assistant if they continue to be bothered by any pictures afterwards. Any subjects expressing continued distress after viewing the pictures will be counseled by a trained staff member or the PI.

*Experience to date in this study:* We have not had any reports of emotional discomfort from questionnaires or pictures.

*2. Confidentiality:* Given the sensitive information collected as part of the study, there are may also be social, legal or economic risks associated with loss of confidentiality. Please see Section 13.2, Subject Confidentiality, for details on steps we take to minimize these risks.

*Experience to date in this study:* We have not had any breaches of confidentiality.

*3. Psychophysiological monitoring:* We will monitor psychophysiological responses using conductive electrodes attached to the skin of subjects with an adhesive. Approximately 50% of subjects report mild discomfort or irritation as a result of cleaning the sites to apply the sensors, but this should be transient, lasting 15min up to an hour. A few individuals experience red marks at the site of application that can last up to one day after the application. A very small number of subjects (approximately 1 in 100) with particularly sensitive skin may experience marks that last longer (up to a week). This risk will be minimized by asking subjects about sensitive skin or previous allergic reactions to skin products and by rigorous training in correct skin cleaning procedures for research assistants. There are also risks of electrical hazard, when subjects are attached to conductive equipment. To reduce this risk, all equipment will be appropriately grounded and shielded, and stimulus equipment will be optically isolated from the subject making any electrical hazard to the subject extremely unlikely. There are infection risks when subjects' skin is in contact with equipment. To reduce this risk, all surfaces placed in contact

with the subjects' skin are disposable, and all equipment will be thoroughly cleaned between sessions.

*Experience to date in this study:* We have not had any reports of serious skin irritation, electrical hazard or infection.

**3. Study Medication.** Dextroamphetamine is extremely well understood in terms of benefits/effects and risks and has been studied extensively over the past 60 years in many populations. It has been investigated in individuals with CUD and other stimulant use disorders in many previous protocols [47,50–53] Previous studies have generally used fixed doses of the extended release preparation proposed here. When administered in a controlled trial, dextroamphetamine carries modest risks overall. We have a current *Investigational New Drug Protocol* for this study (IND #131221).

**Risks During Regular Use:** **Serious but rare risks** of dextroamphetamine include:

1. Heart related problems, including stroke, heart attack and increased blood pressure and heart rate. We protect against this specific risk by requiring a full ECG and physical examination prior to enrollment in the study, with our study physician excluding individuals with contraindicating cardiovascular conditions, and by reviewing subject vitals at each visit. There have been no reported serious adverse cardiovascular events in closely monitored cocaine dependent populations [47,50,51,53–56]. Any individuals reporting symptoms of cardiovascular complications during the study will be immediately evaluated by the study physician to determine treatment needs. 2. Psychiatric problems, including mania, psychosis and aggression. We protect against this risk by excluding individuals with active psychiatric disorders aside from CUD. We additionally monitor for suicidal ideation at every study visit using a validated screening. Psychiatric adverse effects are rare, even in studies of individuals with amphetamine and cocaine use disorders [47,50,51,53–56]. Any individual showing symptoms of mania, psychosis, suicidality or aggression during the study will be immediately evaluated by the PI, a licensed clinical psychologist, to determine treatment needs. 3. Peripheral vasculopathy, including Raynaud's syndrome. Vasculopathy symptoms are generally intermittent and mild, and reverse with discontinuation of the drug. We protect against this risk by excluding individuals with other medical complications that might put them at risk for vasculopathy, and reviewing reported AEs for potential vasculopathy at each visit. There have been no reports of serious vasculopathy in studies of individuals with CUD taking this drug [47,50,51,53–56]. Any individuals reporting symptoms of vasculopathy during the study will be ~~immediately~~ evaluated by the study physician to determine treatment needs.

**More common but less serious risks** include: allergic reactions, blurred vision, fast or irregular heart beat, decreased appetite, restlessness, anxiety, tremors, headache, trouble sleeping, dizziness, stomach upset, weight loss, dry mouth, diarrhea or constipation, impotence, changes in sex drive, frequent or prolonged erections (see attached *Package Insert*). In addition to protections against specific risks of dextroamphetamine outlined above, our general risk protections include: 1. A gradual 1-week run-up under close supervision by study staff. 2. Regular evaluation of adverse events, side effects, vitals and suicidality at each treatment

visit. Our Adverse Events Form includes both open-ended questions and a checklist of common side-effects completed by the subject. *On the open-ended section:* If any key symptoms for heart problems, mania/psychosis or Reynaud's syndrome are spontaneously endorsed, the research assistant will contact the PI (for psychiatric symptoms) or the study physician (for medical symptoms) regardless of reported severity. For any other adverse events/side effects spontaneously endorsed on the open-ended questions, the research assistant will ask additional questions to determine date of onset, pattern, duration and any precipitating events, and degree of interference with life activities. Endorsement of any serious adverse events per FDA criteria, or events that do not meet FDA for an SAE criteria but are endorsed at a "severe" level (upon questioning are interfering with the subject's daily activities) will result in immediate consultation with the PI and study physician. *On the checklist section:* The research assistant will overlay the checklist with a transparency indicating symptoms of particular concern (arrived at in consultation with our study physician) and when to contact the study physician or PI (see Adverse Events Overlay, attached). Of note, any symptom endorsed at a severe level will result in contacting the physician and PI. For vitals, if blood pressure is  $\geq 140/90$  (either systolic or diastolic is exceeded), or resting heart rate is above 100bpm, the RA will hold medication and immediately consult with the PI and study physician. The PI and study physician will make the determination whether to continue, temporarily hold or discontinue medication, and make referrals for any needed medical or psychiatric follow up. In either of these cases, the study physician may also consult our clinical consultant, who is dual-board certified in internal medicine and psychiatry, in the event a second opinion is required. Participants requiring additional medical evaluation to make a determination will be transported to the study physician's office via cab or ride service. Any patient showing signs of an emergent SAE (e.g. fainting, hypertensive crisis) will be transported immediately to the emergency room via ambulance. For suicidality, subjects will also respond to the Columbia Suicide Severity Rating Scale (CSSR-S) at each visit. CSSR-S evaluations will be conducted by staff who have completed training created by the developers of the scale and been certified. Any endorsement of suicidality will result in medication being held and the PI being immediately contacted to evaluate the subject. Labeling for pill bottles will include the PI's telephone number and institutional information, although there has never been an event requiring emergency breaking of blind at the previous study site.

Risks During Withdrawal: There are no known major medical risks to abrupt discontinuation of dextroamphetamine [57]. The withdrawal syndrome consists of dysphoria, irritability, changes in sleep, appetite and craving. We have included a drug taper to avoid the possibility that these withdrawal symptoms might trigger relapse in individuals abstinent at study completion. All reasonable efforts will be made to offer dose tapering to subjects who withdraw early. If someone withdraws due to a positive COVID test, it would be unsafe for us to see them to provide them with a taper. Thus, for the duration of the pandemic, we will issue a sufficient amount of medication for our normal tapering schedule (135mg) to each individual at the start of the treatment month. This will be marked as "for emergency use

under the direction of the physician only". This is similar to our current practice of issuing one day of emergency medication (60mg) in case of missed sessions, which we have been doing without major problems throughout the study. Then, in the event that a participant cannot be safely seen for a run-down, study staff can supervise the participant tapering at home via telehealth, using either phone or UIC-approved tools of WebEx or PHI Zoom. We are aware of the conditions for using these tools (<https://hipaa.uillinois.edu/telehealth-uic/>) and will follow best-practices in the event this is needed. The ART Lab has procedures in place to contact subjects who miss scheduled study visits. These procedures include obtaining initial consent to follow up by telephone, text, e-mail or, if necessary, certified mail to reach the subject or an identified "locator" who can assist in obtaining current contact information. We update this information weekly during the study using our Weekly Locator Form (see attached)

Risks During Pregnancy: Dextroamphetamine is Category C for use during pregnancy. There are no adequate and well-controlled trials to describe the full spectrum of potential toxic effects of dextroamphetamine on the fetus. No pregnant women will be permitted in study and women and men will be advised to use contraceptive measures that we provide at the clinic. Pregnancy tests will be performed at intake and every two weeks during the study. A positive pregnancy test will result in holding study medication, consultation with the study physician, and referral of the patient for medical follow up. Confirmed pregnancy will result in discontinuation of the study medication and referral for other treatment.

Risks in Combination with Other Recreational Drugs. Amphetamine can be safely co-administered with cocaine, the most likely drug combination in our subjects [55]. Previous dextroamphetamine trials [47,50,51,53] in over 200 patients with CUD have not observed hazardous interactions with recreational use of other illicit drugs, or major adverse events, despite the fact that many individuals in these studies were using cocaine and other illicit substances concurrently. Indeed, the dose of dextroamphetamine proposed (60mg) has been used for comorbid cocaine and heroin dependence in combination with methadone over 24-week period with no serious adverse events [51]. However, individuals with current use of amphetamine, >50 lifetime uses of amphetamine, or previous Amphetamine Use Disorder will be excluded, and use of other recreational drugs will be monitored at every check-in visit using breath, urine and self-report measures for potentially hazardous combinations.

**5. Alternative Treatments.** There is also the risk that participating in this study could preclude someone from obtaining alternate, more effective treatment. We believe that our therapeutic interventions provide treatment that is considerably superior to most, if not all treatment opportunities in the community. Nevertheless, we will refer patients to other facilities upon request or when required by other circumstances. We will also conduct regular literature searches on alternative treatments, and in the event that an alternative treatment emerges with clearly superior efficacy, we would suspend the current study and provide all subjects with referrals for this alternative treatment.

*Experience to date in this study:* We have made referrals to other treatment as needed (e.g. if subjects desired to withdraw from the study due to time conflicts). No alternative treatments with better efficacy have emerged.

**Potential Benefits:** Cocaine use leads to devastating consequences on a personal and societal level. Research participation may assist subjects in abstaining from cocaine during treatment and beyond. This project aims to evaluate a new medication/behavioral treatment combination that is expected to be more effective than other approaches. Both the selected medication and behavioral treatment have shown preliminary evidence of benefit in helping patients reduce cocaine use. Further, this study will pilot new approaches to evaluating treatments that may lead to more personalized and effective treatments for CUD. Thus, by taking part in this research subjects will also benefit others with similar problems because this study is designed

identify what types of treatment work best and for whom.

## **8.0 Data Collection and Management Procedures**

Data sources include urine samples, paper forms containing interview and questionnaire responses, electronic records of responses to questionnaires and tasks from screening and Reward Functioning Assessment sessions, video and voice recordings of therapy sessions.

All urine samples will be collected in containers coded with subject number and visit, and disposed of immediately after testing. Paper forms will be kept in locked cabinets in a locked room in the ART Lab. Only the PI and laboratory staff will have access to these paper forms. Wherever possible, subjects will enter information directly into electronic Access databases, or data will be collected automatically by computer programs (e.g. during reward functioning assessment and fMRI sessions). If this is not possible (e.g. for safety forms that require on-the-spot inspection by study staff), trained research assistants will enter data into an existing, relational database. Allowable input values will be restricted to standardized Access entry forms so as to maintain data integrity. All observations will be double-entered to verify accuracy, with any problems detected discussed with the PI. If necessary, re-training of research assistants will be conducted. After the conclusion of the study, therapy session recordings will be transcribed by a HIPAA-compliant service under contract with UIC, and original recordings will be securely deleted. Transcripts will be maintained in the same manner as other electronic study data for future analysis, as language used in therapy can be analyzed to provide insight into processes active during therapy [59]. fMRI session data will also be stored in the same manner on the same secure server. Paper and electronic records of questionnaire and task data will identify study subjects only by a study code, with a separate electronic file (part of our separately established screening protocol and data repository, see separately submitted protocol) linking study codes to identifiable subject information.

Per our separately submitted screening and data repository protocol, we do not plan to delete this separate linking file when data collection is complete. Please see Section 13.2, Confidentiality, and our separate screening protocol for additional details and justification. Thus, coded data will NOT be treated as de-identified. Data will be stored for a minimum of 6 years, in accordance with NIH policy, and may be stored indefinitely.

## **9.0 Data Analysis**

Primary data analysis will be conducted by the PI. As this study is funded by a Career Development Award from NIDA, the PI will also consult with her designated statistics mentor, [name], an expert in Bayesian statistics for clinical trials at the University of Texas Health Science Center at Houston. In the event that [name] needs direct access to the data set in this capacity, the PI will follow the guidelines in Section 13.2, Subject Confidentiality, including complete de-identification, or if this is not possible, implementation of a Data Use and Transfer Agreement.

**Randomization:** Participants will be assigned to conditions via urn randomization for even distribution of past 30 days cocaine use ( $\leq 15$  days vs.  $> 15$  days) and baseline SHAPS score (above vs. below an established clinical cut point for anhedonia).

**Overall Data Analytic Strategy:** The analytic strategy will use parallel Frequentist and Bayesian analyses. Together, these two complementary approaches provide a more accurate evaluation of hypotheses when the sample size is small [60]. In particular, although conventional Frequentist approaches to statistical testing testing permit rejection of the null hypothesis given the observed data or data more extreme, Bayesian analysis permits conclusions regarding the alternative hypothesis: the probability that a subgroup effect of a specified magnitude exists [61,62]. Thus the Bayesian evaluation is considered our primary statistical approach for this initial proof-of-concept study.

Generalized linear modeling and mixed effects models (R v.3.2, WinBUGS v.1.4) will comprise the primary analytic methods. Primary Bayesian analyses will use vague, neutral priors:  $\sim \text{Normal}(\mu = 0, \sigma^2 = 1 \times 10^6)$  for coefficients in the log-form and  $\sim \text{Gamma}(\text{Shape} = 0.001, \text{Inverse Scale} = 0.001)$  for the dispersion term; sensitivity analyses with pessimistic priors will also be conducted to assess robustness of findings. Clinical outcomes will be analyzed on an intent-to-treat basis, with sensitivity analyses of robustness to assumptions about missing data. For each aim, parallel analyses will be conducted in the full study group ( $N = 80$ ) and the sub-set ( $N = 24$ ) with fMRI measures. Significance for Frequentist outcomes will be set at  $p = 0.05$ , and a Bayesian probability of 80% or greater that an effect exists will be considered to merit further consideration.

**Severity Measures:** A composite score of CUD severity will be derived from the summed z-scores of severity from the SCID, TLFB and ASI.

**Anhedonia Measures:** Principal components analysis will be used to determine whether anhedonia measures can be reduced into composites representing consummatory, motivational and reward learning functions, as expected. If this is inappropriate, we will use individual measures with pessimistic priors to address multiplicity.

**Potential Confounds:** Per published guidelines on confounding in clinical trials [63,64], we will assess all major demographic and baseline variables, and those that either differ between treatment groups or correlate with anhedonia, *and* also relate to outcomes (i.e. severity, abstinence) will prompt two sets of analyses, one with the variable as a covariate and one without, to assess confounding.

**Power Analysis:** In a Bayesian framework, the goal of a proof-of concept study is to produce the best possible estimate of an effect's likelihood and size, to aid decision-making. Thus, the sample was selected to be the maximum feasible within the financial means available. Traditional power analysis bears on the probability of a false negative, not the probability the alternative hypothesis is true (the focus of our analysis). However, for thoroughness, we conducted Frequentist power analyses for the full sample ( $N = 80$ ), moderate attrition ( $N = 64$ ), and fMRI sub-sample ( $N = 24$ ). For *Aim 1*, which focuses on the correlation between anhedonia and addiction severity, at  $\alpha = 0.05$  and 80% power, the full sample could detect a small  $r = .31$ , with attrition a small-to-moderate  $r = .34$  and in the fMRI sub-sample a moderate  $r = .6$ . For *Aim 2*, *Preliminary Data* and [19] suggest a range of  $d = 0.68-1.60$  for the effect of anhedonia on Contingency Management outcomes, depending on measure (self-report vs. imaging). At  $\alpha = 0.05$  and 80% power, the full sample could detect a moderate  $d = .64$ , with attrition a moderate  $d = .72$ , and the fMRI sub-sample a large  $d = 1.04$ . For *Aim 3* Monte-Carlo simulation indicated a prohibitively large sample for this award ( $N = 200$ ) would be needed to reach a definitive Frequentist conclusion about a moderately-sized mediational effect. A major advantage of our Bayesian approach is that we will be able to provide information about the likely magnitude of this effect, even in this smaller study.

**Trial Termination Criteria:** Because this study is relatively small (group sizes from 20 – 30), and is designed to test a potential moderator of outcomes in the context of an already established behavioral treatment and off-label use of an FDA-approved drug already suggested to be efficacious for CUD, no interim efficacy analysis is planned and no trial termination criteria are set.

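### Aim 2 power: at the stated sample sizes (80, 64, 24) no single two-sample t-test gives .64, .72 and 1.04, so at least one figure or its N label needs correction

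*Combined protocol and SAP*

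**What the plan says.** The Power Analysis paragraph of Section 9.0 names three samples: full (N = 80), after moderate attrition (N = 64) and fMRI (N = 24). For Aim 2, one statement of alpha = 0.05 and 80% power covers three detectable effects: "the full sample could detect a moderate $d = .64", then "with attrition a moderate $d = .72", then "and the fMRI sub-sample a large $d = 1.04". The expected effect, d = 0.68 to 1.60, is stated "for the effect of anhedonia on Contingency Management outcomes". The paragraph does not give the test, whether it is one- or two-sided, or how the sample divides into the two groups that d compares.

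The same section limits the weight of these figures. On sample size it says that "the sample was selected to be the maximum feasible within the financial means available", and it introduces the calculation with "for thoroughness, we conducted Frequentist power analyses for the full sample". Under Overall Data Analytic Strategy it says "Thus the Bayesian evaluation is considered our primary statistical approach". It also says that for each aim "parallel analyses will be conducted in the full study group" and in the fMRI subset of 24, so the third figure describes a planned analysis.

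**The concern.** Three figures given together under one alpha and one power will be read as comparable, differing only through N. They do not behave that way: 1.04 is too small for N = 24 if .64 and .72 are right for 80 and 64. If 1.04 is the figure at fault, the plan overstates what the fMRI subset can detect. If the fault lies in the N labels, the plan overstates what is known about the full and post-attrition samples and uses a one-sided test without saying so. Either way a reader cannot tell what the planned samples can detect for Aim 2.

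**Working it through.** **Inputs.** From Section 9.0: alpha 0.05, power 80%, N = 80, 64 and 24, stated d = .64, .72 and 1.04. From the Design Overview in Section 3.0: arms of 30, 30 and 20, of which the two CM arms total 60. Assumed, because not stated: a two-sample t-test, with sidedness and split varied.

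**Formula.** With groups n1 and n2, the t statistic is noncentral t on N - 2 degrees of freedom with noncentrality d x sqrt(n1 x n2 / N), which is d x sqrt(N) / 2 for equal halves. The detectable d is the value at which the chance of passing the critical t is 80%.

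**Step 1. Reproduce the plan's figures with equal halves.**

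| | N = 80 | N = 64 | N = 24 |
|---|---|---|---|
| Stated d | .64 | .72 | 1.04 |
| Two-sided, detectable d | .634 | .711 | 1.197 |
| One-sided, detectable d | .561 | .629 | 1.048 |
| Two-sided power at stated d | 80.7% | 80.9% | 68.3% |
| One-sided power at stated d | 88.3% | 88.6% | 79.5% |

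For N = 24 the noncentrality at d = 1.04 is 1.04 x sqrt(24) / 2 = 2.547. The critical t on 22 degrees of freedom is 2.074 two-sided and 1.717 one-sided, which gives 68.3% and 79.5%. The first two figures fit the two-sided test and the third fits the one-sided test.

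**Step 2. A check that needs neither split nor sidedness.** On a fixed basis d x sqrt(N) should be roughly constant and rise slightly as N falls. The stated figures give .64 x sqrt(80) = 5.72, .72 x sqrt(64) = 5.76 and 1.04 x sqrt(24) = 5.09. Scaling .64 alone gives .64 x sqrt(80/24) = 1.17 at N = 24, before the small-sample t correction raises it.

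**Step 3. Let the split vary, with N as stated.** Over splits from 12:88 to 50:50, the smallest worst-case miss across the three figures is .060 (one-sided, 34.8% in the smaller group: .589, .660, 1.100). Two-sided, the smallest miss is .157. Two sets of splits come within .01 of both .64 and .72:
- two-sided, 39.1% to 50% in the smaller group: 1.197 to 1.226 at N = 24;
- one-sided, 24.8% to 26.7%: 1.184 to 1.213 at N = 24.

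Other bases tried at the stated N (a rank test, a correlation converted to d, a logistic per-SD effect) that fit the first two to within about .01 put the third between 1.17 and 1.27.

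**Step 4. Let N vary.** The attrition implied by the plan is 1 - 64/80 = 20%, so the CM arms would fall from 60 to 60 x 0.8 = 48. Equal halves at N = 60, 48 and 24 give:
- one-sided: .650, .729, 1.048;
- two-sided: .736, .826, 1.197.

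The one-sided row is within .01 of all three stated figures and equals them if cut to two decimals. It requires the first two figures to belong to 60 and 48 rather than 80 and 64, and all 24 fMRI participants to be counted as CM participants.

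**Step 5. Size.** Two-sided with equal groups, 80% power at d = 1.04 needs N = 32 (81.2%; N = 30 gives 78.5%). At the top of the expected range, d = 1.60, two-sided power with 12 against 12 is 96.3%.

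**The case against.** The strongest objection is that one basis does match all three figures: the one-sided test on the CM arms in Step 4. It is not far-fetched. The expected effect range is stated for CM outcomes, and the Aim 2 hypothesis is directional and concerns outcome under CM. On that basis 1.04 is about right. This stands, and it rules out a stronger reading that a reader might infer: that the fMRI figure is the proven error and that .64 and .72 are sound. The documents do not support that, because they never state the basis.

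Nor do they establish the CM-only reading. The paragraph labels the samples 80 and 64, Section 3.0 models Aim 2 by treatment group across all arms, and the Aim 1 figures of .31 and .34 fit a two-sided test at 80 and 64 (Fisher z: .309 and .344). If the 24 were spread over the arms in proportion, 24 x 60/80 = 18 would have CM, and the one-sided figure would be 1.225 rather than 1.04. Even if the CM-only reading is true, the text still needs correcting, because the N labels would be wrong and the sidedness undeclared.

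A second objection is that nothing depends on these figures. That largely stands: feasibility set the sample, the power analysis is supplementary and the primary inference is Bayesian. It bears on severity, not on whether the figures agree.

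**Conclusion.** The point holds in a limited form. At N = 80, 64 and 24, no two-sample t-test with a common sidedness and split gives .64, .72 and 1.04, so at least one figure is wrong for its stated N. Two readings remain, and choosing between them is an inference.

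- **(a) The stated sample sizes are right and the test is two-sided.** Then .64 and .72 stand, the fMRI figure should be about 1.20, and power at d = 1.04 with 12 against 12 is 68%. A one-sided test with roughly a quarter of participants in the smaller group leads to the same figure of about 1.2.
- **(b) The figures came from a one-sided test on the CM arms only.** Then 1.04 is about right, but .64 and .72 belong to about 60 and 48 participants. The two-sided values would be about .74, .83 and 1.20.

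Severity is minor. A reader might infer that the fMRI analysis loses its justification, but about 1.2 is still a large effect inside 0.68-1.60. The check assumes a two-group t-test, which only approximates the planned generalized linear model by treatment group.

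**What to change.** Recompute all three Aim 2 figures on one basis and state it: test, sidedness, group split and the N behind each figure.

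- If N = 80, 64 and 24 stand and the test is two-sided, keep .64 and .72 and replace 1.04 with about 1.20.
- If the run was one-sided on the CM arms only, correct the N labels to those used and state the sidedness, or restate two-sided as about .74, .83 and 1.20.

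This is a text correction to one paragraph. Sample size, design and analysis are unchanged. The cost is a slightly less favourable stated figure, or a declared one-sided test.
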